3.2 Safety Variables

The following safety variables will be included for both Part 1 and Part 2:

- Study treatment exposure;
- Treatment-emergent adverse events (TEAEs);
- Clinical laboratory tests including hematology, clinical chemistry, and urinalysis;
- Physical examinations;
- Vital signs;
- 12-lead electrocardiograms (ECGs);
- Condition-specific safety outcomes, including the following:
 - Spasticity. Modified Ashworth Scale (MAS) (Pandyan et al. 1999) is a clinician administered examination for spasticity which measures muscle tone around selected limb joints. The total MAS score will be calculated and summarized for both part 1 and part 2. In addition, for part 2, bilateral total scores for Elbow, Wrist, Hamstrings, Quadriceps, Gastrocnemius, and Soleus will be analyzed to compare between treatment group with control group.
 - Pain. Brief Pain Inventory (BPI) (Cleeland and Ryan 1994) is a selfadministered questionnaire used to assess the severity of a subject's pain and the impact of this pain on the subject's daily functioning. The following scores will be calculated and summarized:
 - BPI pain severity for each of the four severity items ("worst," "least," "average," and "now"). For part 2, mean BPI pain score at Study Day 169 and change from baseline will be analyzed to compare treatment group with control group.
 - BPI pain interference. For part 2, mean BPI pain interference score at Study Day 169 and change from baseline will be analyzed to compare treatment group with control group.

4. Pharmacokinetic variables

- Serum and CSF samples will be collected and analyzed for concentrations of AXER-204 at planned time points following the schedules for Part 1 or Part 2, as described in the protocol.
- Pharmacokinetic (PK) parameters will also be determined (section 8.6.1) using a non-compartmental approach (NCA) for Part 1.

5. Immunogenicity variables

Pre-dose Anti-drug antibody (ADA) serum will be collected for ADA analysis for both Part 1 and Part 2 following the protocol defined schedule. The following immunogenicity variables will be analyzed:

• Anti-drug antibody (ADA) incidence

6. Analysis Population

6.1 All Randomized Set (Part 2)

The All Randomized Set will consist of all randomized Part 2 subjects. Subjects will be analyzed according to their randomized treatment.

6.2 Safety Population (Part 1 and Part 2)

The Safety Population will consist of all subjects treated with at least one dose of study treatment. Safety outcomes will be assessed using the Safety Population. For Part 2, safety outcomes, including the condition-specific safety outcomes as described in section 8.8.7, will be analyzed according to their actual treatment received.

6.3 Full Analysis Set (Part 1)

The Full Analysis Set (FAS) will consist of all subjects who had at least one dose of study treatment and at least one post-baseline ISNCSCI assessment in Part 1. Efficacy outcomes in Part 1 will be summarized using FAS.

6.4 Modified Intent to Treat Analysis set (Part 2)

The Modified Intent to Treat (mITT) Analysis Set consist of all Part 2 subjects who were randomized and had at least one dose of study treatment and at least one postbaseline ISNCSCI assessment. Efficacy outcomes for Part 2 will be evaluated using the mITT analysis set. Subjects will be analyzed according to their randomized treatment.

6.5 PK Analysis Set (Part 1 and Part 2)

The PK Analysis Set will include all subjects who received at least 1 dose of study drug and had evaluable PK data. All protocol deviations that occur during the study will be considered for their severity/impact and will be taken into consideration when subjects are assigned to the PK analysis set. PK analysis will be conducted for PK analysis set. Subjects will be analyzed according to their randomized treatment.

6.6 Antidrug Antibody Analysis Set (Part 1 and Part 2)

The Antidrug Antibody (ADA) Analysis Set will include all subjects who received at least 1 dose of study treatment and had at least one post-baseline ADA. This analysis set will be used to summarize ADA results. Subjects will be analyzed according to their randomized treatment.

6.7 Per Protocol Set (Part 2 only)

The Per Protocol Set (PPS) will be a subset of mITT and consist of subjects who received at least 5 doses (~80%) of the planned cumulative number of doses of study drug and have no important protocol deviations that might impact efficacy assessment.

The important protocol deviations leading to exclusion from the PPS may include but not limited to the following: violation of key inclusion/exclusion criteria, use of prohibited medications as defined by the study protocol or in discussion with the Sponsor and/or medical monitor, errors in treatment allocation, etc. All important protocol deviations leading to exclusion from the PPS will be reviewed and approved by the Sponsor prior to database lock and unblinding. Subjects will be analyzed according to their randomized treatment.

7. DATA Handling

7.1 Time points

Day 1 is defined as the day of the first study treatment administration. Relative days after Day 1 are calculated as (assessment date – Day 1 date) + 1. Relative days prior to Day 1 are calculated as (assessment date – Day 1 date). The day prior to Day 1 is Day -1.

For Part 1, all data will be analyzed using nominal study visits as defined in the Study Schedule in the protocol and eCRF. Data collected at unscheduled visits will not be included in summary tables but will be listed only, unless specified otherwise.

7.2 Visit Window (Part 2)

For part 2, time windows will be defined for both safety and efficacy assessments for summaries and values by visit as well as efficacy analysis. All data for unscheduled and scheduled visits have the potential to be included in the summary and analysis based on the actual date. The window for the visits following baseline will be constructed according to the following convention: the upper limit of the interval falls half way between the 2 visits if odd number of days exists between two consecutive visits. If an even number of days exists between two consecutive visits then the upper limit will be taken as the midpoint value minus 1 days. For example, the visit windows for ISNCSCI assessment are:

- Day 1, visit window NA
- Day 21, visit window 2 42
- Day 63, visit window 43 83
- Day 104, visit window 84 136
- Day 169, visit window 137 211
- Day 253, visit window 212 end of study

If there is more than one value within a visit window then the closest value to the scheduled visit date will be included in the summary and analysis. If 2 events are equal distance from the scheduled visit date then the event with earlier date will be selected for analysis. For listings, all visits including unscheduled visits will be displayed by collected visit name.

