#### 11.2.4. Follow-up Visits 8 and 9 (Study Days 169 and 253)

At Visits 8 and 9 (Study Days 169 and 253), 12-Lead ECGs, physical examinations (abbreviated at Visit 8; full exam at Visit 9, with height/weight), vitals will be performed. Serum samples will be collected for PK and ADA analysis as detailed in Section 13.2. Blood will be collected for laboratory testing and viral serology, and urine collected for urinalysis. Urine pregnancy tests will be conducted for women of childbearing potential. Changes to concomitant medication will be assessed and recorded as well as AEs and SAEs. CSF will be collected at Visit 9 (Study Day 253).

In Study Visits 8 and 9, subjects will have all efficacy and QoL assessments performed (see the Schedule of Events for specifics, Table 6), in the following order:

- ISNCSCI
- GRASSP. Note: GRASSP prehension ability and prehension performance testing will be video recorded.
- Modified Ashworth Scale, fingers and thumb excluded
- SCIM III Self-Care & Mobility subscores
- Brief Pain Inventory
- Neuro-QOL Item Bank v1.0 Upper Extremity Function (Fine Motor, ADL)
- SF-36 v2 Health Survey
- CUE-Q
- PGIC Chronic SCI
- International Standards to document remaining Autonomic Function after Spinal Cord Injury (ISAFSCI)

GRASSP prehension ability and prehension performance testing will be video recorded.

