3.1.2.1.4 Handling of Intercurrent Events

The following intercurrent events are anticipated during the study. Table 3 describes how intercurrent events will be collected and handled within the analysis.

Table 3Handling of Intercurrent Events for the Primary Estimand

Intercurrent event	Data collection and analysis	
Important protocol deviation, including use of prohibited medication, prior to assessment scheduled on Study Day 169	Patients will be followed and data collected after the intercurrent event will be used in analysis in line with the treatment policy strategy, i.e. regardless of the intercurrent event.	
Did not receive at least 5 doses (~80%) of the planned cumulative number of doses of treatment		
Did not perform at least one post- baseline assessment	Patients who experienced the intercurrent event will be excluded from analysis in line with a principal stratum strategy.	
Discontinuation from the study prior to assessment scheduled on Study Day 169	Patient's measurements up until the time of the intercurrent event will be used in analysis in line with the while on treatment policy, i.e. the endpoint is only evaluable in patients who complete the assessment scheduled on Study Day 169.	

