3.1.2.4.3 Endpoint

The endpoint is the Patient Global Impression of Change (PGIC) responder rate at Study Day 169. Patients that have evaluation results including "Much better", "Better", or "A little better" are considered Responders, whereas patients that have evaluation results including "Much worse", "Worse", "A little worse", or "No change" are considered Non-Responders.

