3.1.2.4.4 Handling of Intercurrent Events

The intercurrent events strategy is the same as section 3.1.2.1.4.

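### If the Day 2 start in SAP 7.2's ISNCSCI example is carried over, the Day 169 window for seven instruments is Days 2–211, so an early-termination value could be analysed as the Day 169 result

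*SAP*

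**What the plan says.** **Windows.** SAP 7.2 covers Part 2 safety and efficacy assessments alike. The rule is introduced by "The window for the visits following baseline will be constructed according to the following convention", and what follows says only where each window ends. Values are placed by date: "All data for unscheduled and scheduled visits have the potential to be included in the summary and analysis based on the actual date". The one worked example is ISNCSCI. Its first post-baseline entry is "Day 21, visit window 2 42" (Days 2 to 42) and its Day 169 entry is Days 137 to 211. If several values fall in one window, the one nearest the nominal day is used. Section 7.2 does not mention early-termination (ET) visits.

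**Schedule.** Protocol Table 6 places PGIC, CUE-Q, SF-36, Neuro-QOL, ISAFSCI, Modified Ashworth and BPI at Day 1, Day 169 and Day 253/ET, with nothing in between. Protocol 11.2.4 agrees: "In Study Visits 8 and 9, subjects will have all efficacy and QoL assessments performed". Protocol 9.1 calls for the ET assessments when a subject leaves the study.

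**PGIC.** SAP 3.1.2.4.3 says: "The endpoint is the Patient Global Impression of Change (PGIC) responder rate at Study Day 169". SAP 3.1.2.4.4 says: "The intercurrent events strategy is the same as section 3.1.2.1.4". That brings in Table 3, whose row on leaving the study before Day 169 has two clauses. The first is "measurements up until the time of the intercurrent event will be used in analysis in line with the while on treatment policy". The second is "the endpoint is only evaluable in patients who complete the assessment scheduled on Study Day 169".

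**The concern.** An instrument with no visit between baseline and Day 169 has no earlier window to receive an early value. Under the same rule, a Day 30 ET value goes to Day 21 for UEMS and to Day 63 for GRASSP and SCIM III. For the seven instruments it would go to Day 169, and if it is the subject's only value in that window, the nearest-value rule cannot remove it.

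PGIC asks about change since the trial began, so a Day 30 answer covers about one month and not six. CUE-Q, SF-36, Neuro-QOL, Modified Ashworth and BPI are analysed by the primary MMRM method (SAP 8.5.2.3 and 8.8.7). Day 169 is their only scheduled post-baseline visit in the Day 169 model, so a misplaced ET value would be that subject's whole contribution to it.

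The SAP does restrict post-baseline summaries to scheduled visits for laboratory tests, vital signs and ECG (8.8.3 to 8.8.5). It sets no such limit for these seven instruments.

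**Working it through.** **Rule as applied.** Let k be the number of days strictly between two consecutive visits.
- k odd: upper limit = midpoint.
- k even: upper limit = midpoint rounded up to a whole day, minus 1.
- The first window opens on Day 2, taken from the ISNCSCI example. Each later window opens the day after the previous one closes.

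**1. Reproduce the printed ISNCSCI windows (Days 21, 63, 104, 169, 253).**
- 21 to 63: k = 41, odd; (21 + 63)/2 = 42.
- 63 to 104: k = 40, even; 83.5 rounds up to 84; 84 − 1 = 83.
- 104 to 169: k = 64, even; 136.5 rounds up to 137; 137 − 1 = 136.
- 169 to 253: k = 83, odd; (169 + 253)/2 = 211.

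The windows are 2–42, 43–83, 84–136, 137–211 and 212–end, as printed. Without rounding, the even rule would give 82.5 and 135.5, which do not match. The rounding choice does not affect this point, because the 169-to-253 gap is odd.

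**2. GRASSP and SCIM III (Days 63, 104, 169, 253).** The windows are 2–83, 84–136, 137–211 and 212–end. Their Day 169 window already opens on Day 137.

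**3. The seven instruments (Days 169, 253).** The windows are 2–211 and 212–end.

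**4. Width of the Day 169 window.**
- Seven instruments: 211 − 2 + 1 = 210 days.
- ISNCSCI: 211 − 137 + 1 = 75 days.
- Protocol visit window (169 ± 7, Days 162–176): 15 days.
- Days 2–136, which ISNCSCI does not map to Day 169: 135 of the 210 days (64%).

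**5. Who could be affected.** Only a subject who leaves the study, attends an ET visit before Day 137 and has no value nearer Day 169. Subjects who stop treatment alone stay in follow-up (SAP 7.3.2). If they attend Day 169, that value is selected.

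**6. Effect on PGIC, assuming 16 mITT subjects per arm.** SAP 8.5.2.2 expresses responders as a share of the mITT set, and the SAP's general-principles table (Table 6) makes the analysis population the default denominator. With r responders among the other 15 subjects:
- early answer is a response: (r + 1)/16 − r/16 = 1/16 = 6.25 points;
- early answer is not a response: r/16 − r/16 = 0.

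**The case against.** The strongest reply has five parts.

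- **Days 2–211 is not printed anywhere.** The Day 2 start comes from an example for another instrument. This stands, and the point is conditional on it. Even so, the written rule reproduces every printed ISNCSCI window and offers no other starting day.
- **PGIC already has its own rule.** A specific estimand clause normally overrides a general windowing sentence. The two Table 3 clauses can also be read together: earlier measurements enter the model at their own visits, while Day 169 is evaluable only in completers. This largely stands. A reader might infer a flat contradiction for PGIC, but the documents do not support that. What is missing is a statement in 7.2 or in Table 3 that the exclusion prevails.
- **The other six carry little weight.** CUE-Q, SF-36 and Neuro-QOL are exploratory, ISAFSCI gets a shift table, and Modified Ashworth and BPI are safety measures. This stands and limits the severity.
- **The PGIC denominator is already given.** This stands. A reader might compute shifts on evaluable subjects only, since Protocol 15.3 bases percentages on available data. The SAP specifies mITT for this analysis, so those figures are hypothetical.
- **Day 169 data are already unblinded, and Day 137 is borrowed from ISNCSCI.** Both are true. The first is a reason for disclosure. As to the second, Day 137 is a limit the plan already uses; it still admits values up to 169 − 137 = 32 days early, as it does for ISNCSCI.

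**Conclusion.** The point holds as a minor one. If the example's Day 2 start is carried over, SAP 7.2 gives a Day 169 window of Days 2–211 for PGIC, CUE-Q, SF-36, Neuro-QOL, ISAFSCI, Modified Ashworth and BPI. An ET value from the dosing period could then be analysed as Day 169. For the six instruments other than PGIC, no other clause prevents it. For PGIC, Table 3 most naturally does, but the plan should say so.

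The documents do not give the number of ET visits before Day 137, so the effect may be zero. The 6.25-point figure rests on an assumed 16 mITT subjects per arm and one early response.

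A reader might infer that the primary result is exposed, or that a reported Day 169 result was altered. Neither is supported. The UEMS Day 169 window already opens on Day 137, and nothing in the documents shows that a value was misassigned. The PGIC analysis in SAP 8.5.2.2.1 that assigns no change to subjects who left the study is unaffected.

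**What to change.** 1. In SAP 7.2, open the Day 169 window at Day 137 for the seven instruments, as printed for ISNCSCI. The Day 253 window (Day 212 onward) already follows from the convention and needs no change.
2. Show values from before Day 137 as ET. For Modified Ashworth and BPI, keep them in a separate ET row of the safety summaries, because Protocol 14.2.3 lists increased pain and spasticity as events of special interest.
3. State that the second clause of the Table 3 discontinuation row governs PGIC over 7.2. Confirm that the mITT denominator in 8.5.2.2 and the general-principles table applies to the main PGIC analysis.
4. Record this in section 10 as a clarification made after unblinding, state which mapping the top-line run used, and report results under both mappings if any value is reclassified.

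**Cost:** a paragraph in 7.2, a sentence on PGIC, one added row in two safety summaries and a dated section 10 entry. Day 169 tables need rerunning only if a value moves. The downside is that a few early ET values may leave the Day 169 comparisons, and the change comes after unblinding and must be disclosed as such.

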7.3 Handling of Dropouts and Missing Data

Except for the data specified below, missing data will not be imputed.

7.3.1 Handling of Missing or Incomplete Dates

Incomplete dates (partial or missing dates) for adverse event (AE) and prior/concomitant medications will be imputed. The imputed dates will be used to determine treatment-emergent AEs or prior/concomitant medications. The subject data listings will present the observed data without imputation.

- For partial start dates:
 - If day is missing, then if the month and year of the event are the same as the month and year of treatment start date, the treatment start date will be imputed as the date; otherwise the first day of the month will be imputed;
 - If month and day are missing, then if the year of the event is the same as the year of treatment start date, the treatment start month and day will be imputed as the date; otherwise, 01JAN will be imputed.
- For partial stop dates,
 - if day is missing, then if the month and year of the event are the same as the month and year of treatment end date, the treatment end date will be imputed as the date; otherwise the last day of the month is imputed.
 - If month and day are missing, then if the year of the event is the same as the year of treatment end date, the treatment end month and day will be imputed for the date; otherwise, 31DEC will be imputed.
- For dates completely missing, no imputation will be done.

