Prospective subjects who at the time of screening are taking medications that the Principal Investigator judges may confound efficacy and/or safety assessments (listed in Exclusion Criteria, Section 8.2) must stop them, after signing Informed Consent and receiving instructions on the discontinuation of these medications, two weeks or five half-lives –whichever is longer-prior to investigational product administration. The prospective subject must be willing to discontinue treatment and the Investigator must deem this feasible. The prospective subject taking prohibited medication at the time of screening will be considered eligible at the time of investigational product administration (Visit 2, Study Day 1) provided no reintroduction of the prohibited medication is being considered, the appropriate time window since last administration has elapsed, and the subject continues to meet other eligibility criteria. Subjects must remain off prohibited medications until all assessments are completed in the study. Determination of exclusion due to use of a specific medication from these classes of prohibited medications will be made by the Principal Investigator in conjunction with the Medical Monitor based on medical assessment of factors including the dosage, frequency of use, and medical condition being treated.

Concomitant medications will be coded using the World Health Organization (WHO Drug) Dictionary.

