- Spasticity (Modified Ashworth Scale). A clinician administered examination for spasticity which measures muscle tone. A score of 0-4 is assigned to each muscle group evaluated. Note: Testing will exclude fingers and thumb.
- Pain (BPI). A self-administered questionnaire used to assess the severity of a subject's pain and the impact of this pain on the subject's daily functioning.

Concomitant treatments will be assessed according to the timing of their start/stop dates as they relate to the study drug treatment, as follows:

- Prior. Medications with start AND stop date before date of first dose of study drug or placebo.
- Concomitant. Medications with subject exposure that includes at least one dose of study drug or placebo.
- New-onset medications. Concomitant medications with a start date AFTER the first dose of study drug or placebo. New-onset medications are a subset of the full set of concomitant medications.
- Post-treatment medications. Medications with a start date at least 28 days AFTER the last dose of study drug or placebo.

Changes from pre-treatment will be calculated in a similar fashion as for the efficacy endpoints, but no inferential statistics will be provided for safety endpoints. Shifts from baseline in ECG will be tabulated for heart rate and QTcF. Other endpoints will be assessed according to the scale of the variable.

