8.4.3 Previous and Concomitant Medications

Medications received prior to or concomitantly with treatment will be coded by using the World Health Organization (WHO) Drug Dictionary [Version: Global B3-March 2019 (or a later version if updated during the study)] Anatomical Therapeutic Chemical (ATC) Classification codes.

Prior medications and concomitant medications are defined as follows:

- Prior medications are those with a start date and a stop date prior to the first dose date of study treatment;
- Concomitant medications are those with a start date on or after the first dose date of study treatment, or those with a start date before the first dose date of study treatment and a stop date on or after the first dose date of study treatment or ongoing at the end of study;

Statistical Analysis Plan

• New-onset medications are concomitant medications with a start date after the first dose of study treatment. New-onset medications are a subset of the full set of concomitant medications.

If a medication cannot be classified as "prior" or "concomitant" after applying imputation rules for missing/incomplete dates, it will be classified as concomitant.

Prior medications and concomitant medications will be listed together and summarized separately for the Safety population by dose cohort for Part 1 (or by treatment group for Part 2) and overall.

The number and percentage of subjects using any medication will be displayed together with the number and percentage of subjects using at least one medication within each therapeutic class (ATC-Level 2) and generic term. Tables will be sorted in descending overall frequency by the ATC level and in descending overall frequency by generic term, and then alphabetically.

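### SAP 7.3.1 can impute a start date later than a known stop date, so some drugs and SAEs that ended before first dose are tabulated as concomitant or treatment-emergent

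*SAP*

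**What the plan says.** SAP 7.3.1 gives one start-date rule for adverse events and medications. With the day missing, "if the month and year of the event are the same as the month and year of treatment start date, the treatment start date" is imputed; "otherwise the first day of the month will be imputed". With month and day missing, "if the year of the event is the same as the year of treatment start date, the treatment start month and day will be imputed"; for any other year, 1 January is used. No branch refers to the stop date. The result drives classification: "The imputed dates will be used to determine treatment-emergent AEs or prior/concomitant medications". Listings keep the observed dates.

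SAP 8.4.3 calls a drug prior only if its start and its stop both precede first dose. The first limb of the other class reads: "Concomitant medications are those with a start date on or after the first dose date of study treatment". That limb sets no condition on the stop. A drug that still cannot be classified defaults to concomitant. SAP 8.8.2 makes an event treatment-emergent if it starts on or after the date of first dose.

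Protocol 15.11 defines concomitant by exposure that overlaps at least one dose, and calls events before first dose pre-treatment. Protocol 10.2 makes pre-dose stop dates an expected feature of the data: subjects taking prohibited drugs at screening "must stop them, after signing Informed Consent and receiving instructions on the discontinuation of these medications", at least two weeks before dosing.

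**The concern.** A drug with a known stop before first dose must also have started before first dose. Nothing about its class is uncertain, even if the exact start day is unknown. For a subset of such records the SAP rule discards that information, creates an impossible date order and puts the drug in the wrong table. The same happens to a serious event that began and ended during screening; SAEs are collected from consent, so such records can exist.

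Two planned outputs are at stake: the prior and concomitant medication tables, and the TEAE tables, including the serious TEAE tables. A prohibited drug that was properly withdrawn could be shown as used on treatment. The listing, which shows observed dates, would then contradict the table.

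**Working it through.** The plan states no figure here, so the check applies the rules literally.

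**Worked example, first dose 25 June 2021**

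| Recorded start | Recorded stop | Imputed start | Class under SAP 8.4.3 |
|---|---|---|---|
| JUN2021 | 08JUN2021 | 25JUN2021, 17 days after the stop | concomitant (wrong) |
| 2021 | 01JUN2021 | 25JUN2021, 24 days after the stop | concomitant (wrong) |
| MAY2021 | 08JUN2021 | 01MAY2021 | prior (right) |
| 2018 | 08JUN2021 | 01JAN2018 | prior (right) |

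In the first two rows the imputed start is not before first dose, so the drug fails the prior definition. It is on or after first dose, so the drug meets the concomitant definition. The default for unclassifiable drugs never comes into play, because the drug has been classified, wrongly. A screening SAE with onset JUN2021 and resolution 08JUN2021 takes the same imputed onset and becomes a TEAE.

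**How often a washed-out drug could be caught.** With the day missing, start and first dose must share a calendar month. If the stop is at least 14 days before dosing, first dose must fall on the 15th or later. In 2021 that is 365 − 12 × 14 = 197 dates, and 197/365 = 54.0%.

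The next table averages over all 365 first-dose dates in 2021. It assumes a stop exactly 14 days before first dose and true starts spread evenly over a look-back ending at the stop. Neither assumption comes from the documents.

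| Look-back for true start | Misclassed, day missing | Misclassed, month and day missing |
|---|---|---|
| 30 days | 15.7% | 92.2% |
| 365 days | 1.3% | 46.4% |
| 5 years | 0.3% | 9.3% |

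These are shares of partial-start records with a pre-dose stop, not shares of all medication records.

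**Weight of one record.** If the subject has no other drug in that class, one misfiled subject moves a Part 2 entry by 1/16 = 6.25 percentage points, taking about 16 per arm.

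**Check of the fix.** The true start cannot be earlier than the first day of its recorded month (or 1 January of its recorded year), and the stop cannot be earlier than the true start. So first of month (or 1 January) ≤ true start ≤ stop < first dose. The imputed start then never falls after the stop, and the drug is always prior. The first two rows above become 01JUN2021 and 01JAN2021, both prior. No further cap at the stop date is needed.

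**The case against.** The strongest reply is that imputing Day 1 is a deliberately cautious convention, in line with Protocol 15.4, which asks for a conservative approach to missing AE and medication dates. That stands where the stop is missing, ongoing, or on or after first dose, and the rule should stay for those records. It does not stand where a known pre-dose stop settles the class.

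The second reply is that the trigger is narrow, and this stands. A long-standing drug recorded with an earlier month or year stays prior. With only the day missing, a drug washed out over two weeks must have begun in the month of first dose and ended at least 14 days before dosing. Non-serious events before dosing are not collected as AEs, and SAEs are reported within 24 hours, so partial SAE onset dates should be rare.

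A reader might go further and infer that pain or spasticity drugs begun on study would be hidden. SAP 8.4.3 says "New-onset medications are concomitant medications with a start date after the first dose of study treatment", and Protocol 15.11 has the same category ("New-onset medications are a subset of the full set of concomitant medications"). A start imputed to Day 1 cannot meet that definition. But SAP 8.4.3 plans no new-onset table. Such drugs still count as concomitant by treatment group and appear in listings with observed dates. Increased pain and increased spasticity are adverse events of special interest and are tabulated by arm. The documents therefore do not support a claim that on-study treatment is lost from view.

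A reader might also infer that a withdrawn prohibited drug shown as concomitant would remove the subject from the Per Protocol Set. SAP 6.7 bases exclusion on protocol deviations reviewed before database lock, and nothing ties those to an imputed date.

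**Conclusion.** The rule is wrong for one identifiable set of records: start date partial, matching the month and year (or the year alone) of first dose, with a known stop before first dose. Every such drug is counted as concomitant when it was certainly prior, and every such SAE as treatment-emergent when it was pre-treatment. This follows from the text and needs no assumption.

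The number of such records does not follow from the text. The documents give no count of partial dates, and the percentages in the working depend on assumed start and stop patterns. The issue is minor: it can misstate individual entries in small-arm safety tables, while the listings keep the true dates. Efficacy analyses do not use these dates.

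**What to change.** Amend SAP 7.3.1, for medications and AEs alike:

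- Impute the first-dose date for a matching partial start only when the stop date is missing, ongoing, or on or after first dose.
- If the known stop is before first dose, impute the first day of the recorded month, or 1 January when the month is also missing.
- State the principle that an imputed start never falls after a known stop.

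SAP section 10 already records changes made after the Day 169 unblinding. This change should be dated and labelled there in the same way; the rule itself does not depend on treatment arm. The cost is a few lines of SAP text, one condition in the date-imputation program and a rerun of the affected tables. No new data are needed.

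Add one note to SAP 8.4.3: a start imputed to Day 1 cannot meet the new-onset definition, so that category would need its own rule if it is ever tabulated.
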